Adult women breast cancer survivors who have undergone all the stages related to breast cancer treatment (chemotherapy, radiotherapy, hormone therapy). The study will be carried out in the facilities of the Exercise Physiology Laboratory of the Exercise and Rehabilitation Sciences Institute of the Universidad Andrés Bello, Concepción city, from different community cancer survivors' social groups of the Concepcion, Chile will be invited to participate of this study. The groups will be randomly allocated to an experimental group of high chemotherapy exposure (EG-HCHT, n=15) or to an experimental group of low chemotherapy exposure (EG-LCHT, n=15), that will adhere to 6-weeks of an exercise training program of concurrent training of HIIT plus RT three weekly.

Inclusion criteria: a) breast cancer diagnosed, b) with or without chemotherapy treatment, c) normal weight body mass index [BMI] 18.6 to 24.9 or overweight/obesity condition by BMI 25.0 to 39.9 kg/m², d) age 30 to 75 years, e) with or without other associated co-morbidities (diagnosed of elevated fasting glucose, prediabetes or diabetes, hypertension or prehypertension, or metabolic syndrome, fatty liver or hypercholesterolemia or screened by our research team), f) with or without hormonal therapy, and g) with or without other pharmacotherapy for specific muscle-groups such as morphine patches, morphine droplets or other pharmacological therapy for SOS pain treatment. **Exclusion criteria:** a) history of abnormal ECG, or diagnosis of other cardiovascular condition/history other than hypertension, vasculopathy, b) history of uncontrolled stage 3 of hypertension or hypertensive crisis, c) diabetes complications such as varicose ulcers, nephropathies, d) skeletal muscle abnormalities (e.g., knee, or hip arthrosis, muscle pain), e) using weight loss treatment/pharmacotherapy or being active in exercise training programs (or within the past three months), and f) use other pharmacotherapy that can influence body weight loss, g) respiratory disease type (chronic

obstructive disease), h) kidney disease, i) pregnancy, and j) smoking behaviour or dependence on other substances.

REFERENCES

1. MINSAL. Tabla de resumen de mortalidad por causa, según sexo y región 2023 [Available from: <https://informesdeis.minsal.cl/SASVisualAnalytics/>].
2. WHO. WHO Guidelines on Physical Activity and Sedentary Behaviour. Geneva; 2021.

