
16. Cohen J. *Statistical Power Analysis for the Behavioral Sciences*. 2013.

STATISTICAL ANALYSIS PLAN (SAP): Data will be presented as the mean \pm standard deviation (SD). Normality and homoscedasticity assumptions will be tested by using Shapiro-Wilk tests and homoscedasticity by the Levene test. For those outcomes with normal distribution, paired *t*-test was applied to test differences, while to those with no normal distribution, unpaired *t*-test was applied. Cohen's *d* effect size (<0.2 = negligible, $0.2-0.49$ = small, $0.5-0.79$ = moderate, ≥ 0.8 = large) for interactions that showed statistically significant (16). Each delta (Δ), pre-post changes, of main and secondary outcomes will be calculated in all groups. To test the associations among main vascular outcomes (PWV, FMD, cIMT_{av}, cIMT_{max}) with anthropometric, body composition, metabolic, cardio-vascular outcomes, and physical fitness outcomes, simple linear regression (to parametric) with R² prediction percentage, or the *Rho* Spearman nonparametric correlation (r_s =) will be applied. Statistical analyses will be developed using Prism 8.0 software (Graph Pad, San Diego, CA, United States), and the SPSSTM software 29 version for Windows (IBM SPSS Inc., Chicago, IL, USA). The alpha level will be fixed at ($P \leq 0.05$) for all statistical significance.

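### The SAP picks the paired or unpaired t-test by normality, not by the comparison being made; used on pre-post data, its unpaired test makes real changes in non-normal outcomes easier to miss

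*Combined protocol and SAP*

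**What the plan says.** The rule is in the Statistical Analysis Plan: for "outcomes with normal distribution, paired *t*-test was applied to test differences, while to those with no normal distribution, unpaired *t*-test was applied". The preceding sentence says "Normality and homoscedasticity assumptions will be tested by using Shapiro-Wilk tests", with Levene's test for equal variances. It does not say whether Shapiro-Wilk is run on baseline values, on both time points or on the differences.

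The same section adds: "Each delta (Δ), pre-post changes, of main and secondary outcomes will be calculated in all groups". So every woman contributes a before and an after value. The Methods describe two separate groups, an "experimental group of high chemotherapy exposure (EG-HCHT, n=15) or to an experimental group of low chemotherapy exposure (EG-LCHT, n=15"), both trained for 6 weeks.

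For associations the SAP does name a rank method: "simple linear regression (to parametric) with R² prediction percentage, or the *Rho* Spearman nonparametric correlation". It names none for differences. It ties Cohen's d to significant interactions, but names no model or test that would produce an interaction.

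**The concern.** Pairing is a property of the data. A pre-post change within a woman is paired whatever its distribution. A comparison of the two exposure groups is unpaired whatever its distribution. The SAP lets a normality test decide instead, and answers non-normality with another t-test.

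The sentence does not say which differences it means, and it fails on each reading.

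- **Reading 1, pre-post change.** Outcomes flagged as non-normal lose their pairing. With positively correlated pre and post values, the unpaired standard error is too large and real changes are harder to detect.
- **Reading 2, the unpaired test is meant for between-group comparisons.** The loss of pairing no longer applies. But non-normal outcomes then have no pre-post test, normal outcomes have no between-group test, and non-normality is still met with a t-test. If the paired test were used between the groups for normal outcomes, there would be no true pairs, and the result would depend on the order of the rows.

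No other sentence names a test of difference, so this one governs every outcome, including the main vascular ones (PWV, FMD, cIMT). Gaps left here would be filled after the data are seen.

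**Working it through.** The plan states no power, effect size, SD or pre-post correlation, so there is no figure of its own to reproduce.

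**Inputs from the documents.** 15 women per group (Methods); 5% significance level (SAP: "The alpha level will be fixed at ($P \leq 0.05$) for all statistical significance"). **Assumed.** Two-sided tests, no dropout, and the correlations, effect sizes and skewness shown below.

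**1. Standard error.** With common SD σ and pre-post correlation ρ, the mean change has variance 2σ²(1−ρ)/n. The unpaired test uses 2σ²/n. The ratio of standard errors is 1/√(1−ρ): 1.41, 1.83, 2.24 and 3.16 at ρ = 0.5, 0.7, 0.8 and 0.9.

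**2. The ignored pairing alone (normal data, n = 15).** Paired power comes from the noncentral t with standardised change d/√(2(1−ρ)). For d = 0.5 and ρ = 0.7 this is 0.5/√0.6 = 0.645, noncentrality 0.645 × √15 = 2.50, power 64%. The unpaired t-test on the same simulated data has 15%. With no true change, its type I error is 0.8% at ρ = 0.5 and 0.1% at ρ = 0.7, not 5%.

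**3. The whole rule on skewed data (reading 1).** Simulation: n = 15, lognormal with log-scale SD 0.6, additive change of 0.8 SD of the differences, 10,000 data sets per setting. The unpaired t-test is used when Shapiro-Wilk gives P ≤ 0.05, otherwise the paired t-test.

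| Power at pre-post correlation | 0.5 | 0.7 | 0.8 | 0.9 |
|---|---|---|---|---|
| SAP rule, either time point checked | 68% | 51% | 40% | 34% |
| SAP rule, baseline checked | 71% | 59% | 51% | 44% |
| SAP rule, differences checked | 78% | 73% | 68% | 65% |
| Paired t-test throughout | about 82–84% | same | same | same |
| Wilcoxon signed-rank throughout | 87–88% | same | same | same |

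Share of data sets flagged: 64–74% with either time point checked, about 50% with baseline, 26–28% with the differences. Type I error of the rule is about 1.8–3.5%. At zero correlation its power is 84–85%, against 86–87% for signed-rank.

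If the raw change is held at 0.8 SD instead, the rule (either time point) gives 67%, 71%, 73% and 74%, against 87%, 97%, 99% and 100% for signed-rank.

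**4. Sensitivity.** With the correlation defined on the log scale, the either-time-point row becomes 71%, 55%, 44% and 34%. With stronger skew (log-scale SD 0.8), d = 0.5 and underlying correlation 0.7, power is 34% unpaired, 68% paired and 78% signed-rank. At correlation −0.3 with normal data the direction reverses: the unpaired type I error is 8.3%.

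**5. Reading 2.** With 15 per group, lognormal-shaped changes and groups 0.8 SD apart, the unpaired t-test has 62% power and Mann-Whitney 76%.

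**The case against.** The best reply is that the sentence is a drafting slip for rank tests. It says 'was applied' where the text around it uses the future tense, and Spearman appears nearby. That is possible, but the text does not say so, and a reader following it would run the wrong test.

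Four further points have some force.

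- **The size rests on assumptions.** Nothing in the documents shows that PWV, FMD or cIMT are as skewed as the illustration, and truly normal outcomes would seldom be flagged. If Shapiro-Wilk is run on the differences, the loss is much smaller. This stands: the case rests on the logic of the rule, and the figures only illustrate it.
- **Signed-rank is a generous benchmark.** This also stands. Against the paired t-test the gap is about 4–5 points narrower, so most of the loss still comes from ignoring the pairing.
- **The reading 1 error is conservative.** True when pre and post values are positively correlated, the ordinary case for one woman measured 6 weeks apart. It is not true for negative correlation.
- **The SAP never states a between-group test.** Correct. That comparison is inferred from the two groups, the changes calculated in each, and the reference to interactions. Without it, reading 1 remains.

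**Conclusion.** The concern holds and must be fixed. The rule selects tests by the wrong criterion, and nothing elsewhere in the documents repairs it.

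On reading 1, with positive pre-post correlation, the consequence is lost power in flagged outcomes rather than false benefit. The loss ranges from negligible at zero correlation to more than half of the available power at a correlation of 0.9, and it depends on which values are checked for normality. Correlation, skewness and effect size are all assumed, so the documents support a range and not a single figure. On reading 2 the consequence is that planned comparisons have no specified test. Confidence in the defect itself is high.

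**What to change.** Replace the sentence with:

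> The comparison determines the test. Within-group pre-post change: paired t-test, with normality assessed on the within-woman differences; Wilcoxon signed-rank if Shapiro-Wilk on those differences gives P ≤ 0.05. Between-group comparison of changes (EG-HCHT vs EG-LCHT): unpaired t-test on the deltas; Mann-Whitney if Shapiro-Wilk on the deltas gives P ≤ 0.05 in either group.

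A simpler alternative has no switch: use these t-tests for every outcome and report signed-rank and Mann-Whitney for every outcome as sensitivity analyses. Either version also gives the SAP's reference to interactions a test, because with two groups and two time points the unpaired t-test on the deltas is the group-by-time interaction.

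The cost is one SAP sentence, with no extra data or patients. In the skewed illustration the signed-rank switch gives 86–87% power and 4.8–5.3% type I error. Its downside is that the data still choose the test at n = 15, and signed-rank inference about a typical change assumes roughly symmetric differences. If the differences themselves are strongly skewed (lognormal shape, log-scale SD 0.6, mean change zero), type I error for the mean is about 10% with the switch and 8% with the paired t-test alone. The alternative avoids the data-driven choice.

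### The association grid (four vascular outcomes by five domains, at least 20 tests) falls under a blanket P ≤ 0.05 rule with no multiplicity control and no exploratory label

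*Combined protocol and SAP*

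**What the plan says.** The Statistical Analysis Plan sets out the association analysis in one sentence. Its aim is given as "To test the associations among main vascular outcomes (PWV, FMD, cIMT_{av}, cIMT_{max}) with anthropometric, body composition, metabolic, cardio-vascular outcomes, and physical fitness outcomes". The method is "simple linear regression (to parametric) with R² prediction percentage, or the *Rho* Spearman nonparametric correlation", so each vascular outcome is paired with one other variable at a time. The section closes with a rule that makes no exception for this analysis: "The alpha level will be fixed at ($P \leq 0.05$) for all statistical significance".

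The Methods give two groups of 15 women, 30 in total.

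The documents do not state:
- how many variables each domain contains;
- whether associations are run in the pooled sample or by group;
- whether they use baseline values, final values or changes;
- whether tests are one- or two-sided.

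There is no multiplicity adjustment, hierarchy, named priority association or exploratory label.

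**The concern.** A per-test threshold of 0.05 applied across a grid produces significant cells by chance at a rate of one per 20 cells when nothing is related. The difficulty comes from a rule the SAP states, not only from detail it leaves out: the rule makes every cell with P ≤ 0.05 a finding.

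Two features add to the risk. In samples this small, a chance cell has to be large to reach significance, so it looks convincing. The regression results will also be expressed as a percentage of variation predicted, which makes a chance cell easy to read as a substantive link between vascular health and fitness, body composition or metabolism. The background sections say that vascular evidence in cancer survivors is scarce, so there is little outside evidence against which to check a spurious link.

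This family of tests is separate from the tests of pre-post or group differences. Naming one primary outcome or contrast for those would leave the grid as it is.

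**Working it through.** The plan gives no error rate or test count for this analysis, so there is no stated figure to reproduce.

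**Inputs from the documents.** Four vascular outcomes (PWV, FMD, average and maximum cIMT), five predictor domains and a threshold of 0.05 per test (all SAP); 15 women per group, 30 in total (Methods).

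**Assumptions.** At least one variable per domain, two-sided tests, bivariate normal data and no true association in any cell. The documents give no correlations, so a range is used.

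**Step 1: number of tests.** 4 × 5 = 20 at the minimum. Running the grid in each group gives 2 × 20 = 40. Two variables per domain in the pooled sample gives 4 × 10 = 40.

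**Step 2: expected false cells.** 20 × 0.05 = 1.0; 40 × 0.05 = 2.0. These do not depend on the correlations.

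**Step 3: at least one false cell, independent tests.** 1 − 0.95^20 = 0.64; 1 − 0.95^40 = 0.87.

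**Step 4: at least one false cell, correlated variables.** Null data were simulated (10,000 to 20,000 sets per setting) with a common correlation within the vascular set and within the predictor set, and none between the sets:

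| Setting | Correlation 0 | 0.5 | 0.8 |
|---|---|---|---|
| 30 pooled, 20 tests | 0.64 | 0.49 | 0.27 |
| Two groups of 15, 40 tests | 0.87 | 0.75 | 0.49 |
| 30 pooled, two variables per domain, 40 tests | 0.87 | 0.68 | 0.36 |

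A repeat run of the second row gave 0.88 / 0.74 / 0.50. That row can also be checked by hand, because the groups are independent: at correlation 0.5, 1 − (1 − 0.49)² = 0.74.

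**Step 5: a different correlation structure.** A second simulation (8,000 sets) made the two cIMT measures nearly duplicate (correlation 0.9 or 0.95) and varied the other correlations from 0.2 to 0.7. For 20 tests in 30 women it gave 0.57 (mild), 0.54 (moderate), 0.46 (strong) and 0.32 (very strong). Spearman in the moderate setting gave 0.55, so the choice of test matters little. Two variables per domain gave 0.78, 0.74, 0.60 and 0.41 for the same four settings.

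**Step 6: how large a chance cell looks.** The smallest significant correlation is |r| = t / √(n − 2 + t²), with t the 97.5% point on n − 2 degrees of freedom.
- n = 30: 2.048 / √(28 + 2.048²) = 0.36, so R² is at least 0.36² = 13%.
- n = 15: 2.160 / √(13 + 2.160²) = 0.51, so R² is at least 0.514² = 26%.

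**Step 7: what formal adjustment would do.** Benjamini-Hochberg at 5% over the whole grid held the chance of any false cell to 3% to 6% under the null. For a lone true signal it demands about 0.05/20 = 0.0025 with 20 tests, which raises the required |r| at n = 30 from 0.36 to about 0.53. With 40 tests and n = 15 per group the threshold is 0.05/40 = 0.00125, or |r| of about 0.75. Simulated power for a lone true r = 0.5 falls from about 0.83 to 0.43 (20 tests, n = 30) and from about 0.50 to 0.08 (40 tests, n = 15 per group).

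**The case against.** The strongest reply is that the analysis is peripheral. The single general objective concerns the effect of adding exercise; no objective, hypothesis or decision rests on an association, and these tests come after the tests of differences. This stands, and it limits the weight of the point. It does not remove it, because the SAP gives the grid the same significance rule as everything else and does not call it exploratory.

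A second reply is that the probability depends on things the documents do not give. That also stands. A reader might infer that a false association is simply as likely as not. The documents do not support so flat a statement: 49% needs one variable per domain, pooling and a correlation of 0.5 within both sets, and under stronger correlation the figure falls to 27%. The two cIMT measures are summaries of one measurement, so strong correlation is plausible in that part of the grid. More variables or separate group analyses push the other way.

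Third, the complete null is doubtful, since some vascular and other cardiovascular measures may well be related. If some links are real, fewer than 1.0 false cell per 20 is expected. This is fair, but the cells that remain null are still tested at 0.05 each.

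Fourth, a reader might infer that the report will present chance cells as findings and leave no way to judge them. The report is not written, and the SAP does plan to show R² or the rank correlation, so strength will be visible. What the plan lacks is narrower: intervals, the number of tests and an exploratory label.

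Last, compulsory adjustment would leave little power in an analysis meant to generate hypotheses. The power figures bear this out, so adjustment should be a choice.

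**Conclusion.** The point holds, with moderate consequence. As written, the SAP makes each of at least 20 association tests a significance claim at P ≤ 0.05, without control or an exploratory label. With one variable per domain, 30 women pooled, two-sided tests and no true associations, about 1.0 false cell is expected and the chance of at least one is 27% to 64% (49% at correlation 0.5). For 40 tests in two groups of 15 it is about 49% to 88%. Even the lowest value is more than five times 5%.

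The exact figure cannot be fixed, because the number of variables, the pooling and the correlations are not stated. A reader might go further and infer that the trial's conclusion about exercise is compromised. It is not: the grid does not enter the estimates of that effect.

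**What to change.** Amend the SAP in four respects:

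1. Exempt the association analysis from the P ≤ 0.05 significance rule.
2. Label it exploratory and hypothesis-generating.
3. Report every cell of the grid with r (or r_s) and its 95% CI.
4. State the number of tests performed and how many would be expected to reach P ≤ 0.05 by chance (5% of them).

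Optionally, if the sponsor wishes to declare any cell associated, apply Benjamini-Hochberg at a 5% false discovery rate over the whole grid: all vascular outcomes, all predictors and all groups analysed.

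The cost is a few sentences in the SAP and a full results table, with no new data or participants. The downside is that nominally significant cells can no longer be presented as findings. The optional adjustment also carries the power loss shown in the working, which is severe if the grid is run separately in each group of 15.

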RESEARCH PROBLEM: Despite the “solid” evidence in favor of the effects of exercise training in breast CS to improve variables such as anxiety, depressive symptoms, fatigue, quality of life, lymphedema and physical function, however, unfortunately, the effects of exercise training on cardio-vascular and metabolic variables, there is still unknown the effects of concurrent exercise training including HIIT plus RT in lower 1RM doses in CS women at level of their cardio-vascular and metabolic health.

This is due to the fact that year after year there is an increase in the number of early diagnoses, as well as an increase in the number of CS with a successful completion of their breast cancer treatment (Radiotherapy, Chemotherapy, Hormonal Therapy), which also leads as an effect to an inherent increase in the number of CS persons, requiring the insertion of this population back into active life. Another effect of the scientific rationale lies in the scarce offer of physical activity and/or exercise training programs for this population of women between 40 and 70 years of age, which would be significantly overcome with the application of the present intervention project that would report cardiovascular, metabolic, physical condition, quality of life and eating patterns variables. **OBJECTIVES; GENERAL:** To determine the effects of traditional therapy added to physical exercise on cardio-vascular, metabolic and physical fitness in female breast cancer survivors who received lower (≤ 7 sessions) and higher (≥ 8 sessions) of chemotherapy.

This study will follow the CONSORT guidelines for randomised trials, will be developed in accordance with the Declaration of Helsinki (2013), and has been approved by the BIOETICAL COMMITTEE OF UNIVERSIDAD ANDRES BELLO (Approval 005/2024 of April 12th). **Design:** An experimental clinical randomized study. **Methods:**

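### Cohen's d is tied to significant interactions that the plan never defines; if the trigger means any significant test, the reported d overstates small and moderate effects, and the four main vascular outcomes have no named primary

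*Combined protocol and SAP*

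**What the plan says.** All the analysis rules are in the Statistical Analysis Plan paragraph.

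- **Effect size.** After the t-tests, Cohen's d is listed with four size bands (0.8 or more is large) "for interactions that showed statistically significant". The tests planned are t-tests, simple linear regression and Spearman correlation. None is described as an interaction test, and the SD that divides d is not named.
- **Contrast.** For normally distributed outcomes a "paired *t*-test was applied to test differences"; other outcomes go to an unpaired t-test. Which differences are meant, within or between groups, is not said. The SAP adds that "pre-post changes, of main and secondary outcomes will be calculated in all groups".
- **Outcomes.** The sentence on associations names "main vascular outcomes (PWV, FMD, cIMT_{av}, cIMT_{max" in no order. The general objective gives domains only: effects "on cardio-vascular, metabolic and physical fitness in female breast cancer survivors". No primary outcome appears anywhere.
- **Alpha.** "The alpha level will be fixed at ($P \leq 0.05$) for all statistical significance". There is no multiplicity rule and no exploratory label.
- **Design (Methods).** Two groups of 15, both in a program "that will adhere to 6-weeks of an exercise training program of concurrent training of HIIT plus RT three weekly". No group without exercise is described.

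**The concern.** An effect size is most useful when it is reported whatever the test result. If d appears only beside a significant p-value, the estimates that readers see are those that happened to come out large. At 15 per group the cut-off is high, so a small true effect can be reported only as a moderate or large one. Anyone who sizes a later trial from such a d would make that trial too small.

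The missing primary adds to this. With several main outcomes, two groups and one per-test alpha, a vascular benefit could be claimed from whichever test reaches 0.05. Because both groups exercise, such a claim would rest on pre-post change.

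**Working it through.** The plan states no power, target effect, SD or familywise error rate, so there is no figure of its own to reproduce.

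**Inputs from the documents:** n = 15 per group; alpha 0.05; four main vascular outcomes; two groups.

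**Assumptions:** two-sided tests, normal data, true d from 0.3 to 1.2, correlation between outcomes from 0 to 0.8, pre-post correlation r of 0.8 or 0.9 where a raw-score SD is used.

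**1. Smallest d that can be significant (SD of change).**
- Pre-post in one group: t(0.975, 14)/√15 = 2.145/3.873 = 0.554.
- Between groups: t(0.975, 28) × √(2/15) = 2.048 × 0.365 = 0.748.

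If significance is the condition for reporting, no smaller d can appear.

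**2. Mean reported |d| divided by true d** (simulated t statistics, 400,000 trials per setting).

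| True d | Pre-post, n = 15: if significant | Pre-post: all trials | d reported | Between groups: if significant | Between: all trials | d reported |
|---|---|---|---|---|---|---|
| 0.3 | 2.5 | 1.17 | 19% | 3.2 | 1.3 | 12% |
| 0.5 | 1.6 | 1.07 | 44% | 2.0 | 1.09 | 26% |
| 0.8 | 1.2 | 1.06 | 82% | 1.4 | 1.03 | 56% |
| 1.2 | 1.06 | 1.06 | 99% | 1.1 | 1.03 | 89% |

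The all-trials columns are the baseline. Their excess over 1 is ordinary small-sample bias plus, at small d, the effect of taking absolute values. The effect of the filter is the gap between the two columns. Between groups, a true 0.5 is reported on average as 0.5 × 2.0 = 1.0, which is large on the SAP's own scale.

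**3. If d uses a raw-score SD instead.** The SD of change is then √(2(1 − r)) raw SDs: 0.632 at r = 0.8 and 0.447 at r = 0.9. The pre-post cut-off falls to about 0.554 × 0.632 = 0.35, or 0.554 × 0.447 = 0.25. At true d 0.3 the within-group ratio is about 1.6 (r = 0.8) or 1.25 (r = 0.9), against about 1.06 unfiltered. At d of 0.8 or more the filter adds almost nothing.

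**4. Unranked outcomes, all nulls true.**
- Four outcomes × two groups, all by paired t-test: 1 − 0.95^8 = 33.7% if independent. Simulated at correlation 0.5 and 0.8: 29% and 22%.
- One between-group test per outcome: 1 − 0.95^4 = 18.5% if independent, falling to about 12% at correlation 0.8.
- The SAP sends non-normal outcomes to an unpaired t-test. Applied to pre-post data at n = 15 under the null, that test rejects about 0.8% of the time at r = 0.5 and about 0.02% at r = 0.8. Each outcome handled that way lowers the first figure.

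**The case against.** The strongest reply on d is that nothing is filtered. The plan contains no interaction test, so the condition is never met; the sentence also has no verb and does not say that d is given for significant results alone. This stands as far as it goes. A reader might infer that the plan as written certainly biases d upward, and the documents do not support that. They support an undefined trigger with two readings: one yields no d at all, the other a biased one. Both need correcting.

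The size also depends on the denominator, which is not stated. At true d 0.3 within a group, the ratio runs from 2.5 down to 1.25 on that choice. This stands, and is a reason to state the denominator.

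On multiplicity, three objections hold in part. The four outcomes are named in the sentence on associations, so treating them as the whole confirmatory family is an inference: the objective also covers metabolic and fitness outcomes. The 22-34% requires paired tests throughout. And a 30-person study with no power or familywise claim need not adopt Holm or a gatekeeping procedure. A reader might infer that the trial has a fixed error rate of 22-34% and must adjust for it. The documents support neither. What remains is that no primary is named and no exploratory label is given, so nothing limits which result may carry a claim.

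**Conclusion.** The point holds in conditional form. The rule for Cohen's d cannot be carried out as written. If its trigger means any significant planned test, it inflates the reported d for small and moderate effects by the factors in the table, given the SD of change as denominator and two-sided tests at 15 per group. The inflation is modest or negligible for large effects, and smaller throughout with a raw-score SD at high pre-post correlation. Because the means, SDs and deltas are planned whatever the p-value, the data summaries themselves are not biased; the problem is confined to d.

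The lack of a primary outcome or contrast is a real but secondary gap. Its size of 22-34% is an illustration under assumed correlations and paired testing, not a property that the plan fixes.

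**What to change.** **1. Effect size.** Replace the phrase "for interactions that showed statistically significant" so that the sentence reads: *Cohen's d, with its denominator stated, and its 95% CI will be reported for every main and secondary outcome regardless of p-value.* This costs SAP wording and a few table columns.

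**2. Primary or exploratory.** Before the data are analysed, the sponsor should do one of two things: name one primary outcome and one contrast (pre-post change, or between-group difference in change), or label all tests exploratory and make no claim from a single significant result. The first option costs the freedom to rest the main claim on another outcome if the primary fails; the second gives up confirmatory claims. Whether to add Holm or gatekeeping, and which outcomes rank as secondary, is for the sponsor to decide.

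Neither option makes a pre-post change attributable to exercise when no group without exercise is described.

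### The SAP labels the in-sample R² of one-predictor regressions on 15 or 30 women as prediction, which that statistic does not measure at this sample size

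*Combined protocol and SAP*

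**What the plan says.** The Statistical Analysis Plan (SAP) section sets an association aim: "To test the associations among main vascular outcomes (PWV, FMD, cIMT_{av}, cIMT_{max"), to be related to five families of variables, "with anthropometric, body composition, metabolic, cardio-vascular outcomes, and physical fitness outcomes". Where data are judged parametric, the tool is "simple linear regression (to parametric) with R² prediction percentage"; otherwise it is a Spearman rank correlation. One significance threshold, P ≤ 0.05, covers everything.

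The Methods give the sample: "an experimental group of high chemotherapy exposure (EG-HCHT, n=15") and "an experimental group of low chemotherapy exposure (EG-LCHT, n=15"), so 30 women in total.

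The SAP does not say:
- whether the regressions are run within each group (n=15) or pooled (n=30);
- whether R² will carry an interval or an adjustment;
- whether any check outside the fitting sample is intended.

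It gives no expected R² and no number of variables per family.

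**The concern.** Least squares chooses the line that makes R² as large as it can be in the women at hand. Prediction means how well that line does in women who were not used to fit it. In large samples the two nearly coincide. With 15 or 30 women they do not, and the in-sample figure is on average the larger.

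A report that follows the SAP's wording would therefore say that a fitness or metabolic measure predicts a given percentage of PWV, FMD or cIMT. A reader would take that as a statement about other survivors, which the calculation cannot supply. The SAP calls these its main vascular outcomes, so such a sentence could well be quoted.

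**Working it through.** **Inputs.** n=15 or 30 (Methods). Alpha 0.05 (SAP), taken as two-sided because sidedness is not stated. One predictor per regression (SAP). Population R², written ρ², is not in the documents and is varied from 0% to 25%. Bivariate normality, independent women and no dropout are assumed. The plan gives no figure of its own to reproduce.

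**1. Average R² in the fitting sample.** With no relation, the mean is 1/(n-1): 1/14 = 7.1% and 1/29 = 3.4%. For ρ² above zero it was simulated (100,000 data sets per setting).

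**2. Average R² of the fitted line in new women.** The expected squared error of a line fitted on n women is (1-ρ²) × k in units of the outcome variance, with k = (1+1/n)(n-2)/(n-3), so the average new-sample R² is 1 - (1-ρ²)k.
- n=15: k = (16/15)(13/12) = 1.156. At ρ²=10%: 1 - 0.90 × 1.156 = -4%.
- n=30: k = (31/30)(28/27) = 1.072. At ρ²=10%: 1 - 0.90 × 1.072 = +4% (rounded).

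The simulation agrees with this formula at every setting. The table shows simulated means; each gap is the difference of the two columns before it.

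| ρ² | n=15: reported | n=15: new women | gap | n=30: reported | n=30: new women | gap |
|---|---|---|---|---|---|---|
| 0% | 7.1% | -15.6% | 22.7 | 3.4% | -7.1% | 10.5 |
| 5% | 11.2% | -9.8% | 21.0 | 8.0% | -1.8% | 9.8 |
| 10% | 15.4% | -4.1% | 19.5 | 12.5% | +3.5% | 9.0 |
| 25% | 28.0% | 13.3% | 14.7 | 26.4% | 19.7% | 6.7 |

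A negative value means that the line does worse in new women than simply using the mean.

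**3. Precision.** The smallest significant R² is t²/(t²+n-2).
- n=15: t = 2.160, R² = 4.667/17.667 = 26.4%, r = 0.514. Fisher z: atanh(0.514) = 0.568, half-width 1.96/√12 = 0.566. The interval for r is 0.002 to 0.812, so for R² about 0% to 66%.
- n=30: t = 2.048, R² = 4.196/32.196 = 13.0%, r = 0.361. The half-width is 1.96/√27 = 0.377. The interval for r is 0.001 to 0.638, so for R² about 0% to 41%.

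**4. Effect of adjusting.** Adjusted R² is 1 - (1-R²)(n-1)/(n-2). The two threshold values become 1 - 0.736 × 14/13 = 20.8% (from 26.4%) and 1 - 0.870 × 29/28 = 9.9% (from 13.0%). Adjusting aims at the population R². It is still not the performance of the fitted line in new women, which step 2 shows to be lower.

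**The case against.** The best defence is that the SAP's purpose is association. No prediction equation or use in new patients is planned, and the phrase may simply be a loose way of saying percentage of variance explained, which R² does give for the sample. As an estimate of the population R² the bias is modest: at ρ²=10%, about 5 points at n=15 (15.4 - 10) and 2.5 at n=30 (12.5 - 10). This stands, and it makes the defect one of labelling and missing uncertainty, not of the wrong model. It does not rescue the label, because the text says prediction.

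Three stronger readings are tempting, and the documents do not support them.

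- **A near-worthless predictor would be reported as predicting 13% to 39%.** That range joins the average over all results at n=30 to the average over significant results only at n=15, both at an assumed ρ² of 10%. Such a predictor is not valueless; what fails is a line fitted on so few women. With no relation at all, the usual value is 3% to 7%, and 39% or more occurs in about 1.3% of data sets at n=15 and under 0.1% at n=30.
- **Only significant R² values will be shown.** The SAP does not say so. If it happened, the overstatement would be worse (at ρ²=10%, averages of 39% at n=15 and 23% at n=30), but that is a reporting practice the plan leaves open, not one it states.
- **Every reported figure will be too high.** At ρ²=10%, the sample R² falls below the population value in 47% (n=15) to 49% (n=30) of data sets. It falls below the fitted line's own new-sample R² in 18% and 29%. The overstatement is an average.

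**Conclusion.** The point holds as a matter of labelling and reporting. An in-sample R² from 15 or 30 women is presented as prediction, with nothing in the plan to support that description. Over population R² of 0% to 25%, the average overstatement against performance in new women is about 15 to 23 points at n=15 and 7 to 11 points at n=30. The range over ρ² replaces a figure the documents do not give. The choice between the two sample sizes is open because the SAP does not settle it. The imprecision matters as much as the average: at either sample size, a just-significant result is compatible with almost no association.

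The results also rest on normality, a two-sided test and full follow-up; dropout would widen the gap. The pre-post comparisons are not affected. The change is worth making because it costs almost nothing, but it does not threaten the trial's general objective.

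**What to change.** In the SAP section:

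1. Replace "simple linear regression (to parametric) with R² prediction percentage" with simple linear regression reporting the variance explained in this sample (R², with adjusted R²).
2. Report the correlation coefficient, Pearson or Spearman, with its 95% confidence interval for every pair tested, whether or not P ≤ 0.05. Regression slopes would not serve as a common measure, since PWV, FMD and cIMT have different units.
3. State whether each regression uses 15 or 30 women.
4. State that no prediction claim will be drawn from these models.

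Relabelling a leave-one-out R² as prediction is not a safe substitute. Among significant results at n=15 and ρ²=10%, it averages about +18% while the true new-sample figure averages about -11%.

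The cost is a few lines of SAP text and a few minutes per model, with no new data. The stated percentages become slightly smaller, and their imprecision becomes visible.
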